#### Hyperglycemia/Hypoglycemia

Cases of new onset and worsened events will be recorded as AEs and will be summarized using appropriate SOC. These events will be summarized by severity and relationship to study drug for each treatment group.

#### **Renal Safety**

Baseline eGFR and values of CK will be summarized by treatment group and by baseline eGFR categories. Shift tables of eGFR category from baseline over the study, will be provided by treatment group.

#### Neurocognitive Events

Neurocognitive events will be identified and evaluated by routine safety monitoring of PE findings and AEs. Neurocognitive events will be summarized using pre-specified MedDRA terms by treatment group.

#### Metabolic Acidosis

Metabolic acidosis events will be monitored by clinical safety laboratory chemistries. These events will be summarized by treatment group.

Confidential

Page 23 of 38

#### 5.5.3 Laboratory Evaluations

Continuous laboratory parameters (serum chemistry, hematology, coagulation, urinalysis, urinalysis [microscopic]) listed in Table 2; fasting serum glucose, and HbA1c will be summarized using descriptive statistics for the observed value and the change, percent change from baseline. Missing values for any of the safety laboratory evaluations will not be imputed; that is, only observed case data will be used. Baseline is defined as the last value prior to the first dose of study medication. Categorical urinalysis data will be listed, but will not be summarized.

As part of the AESI evaluation, below safety lab abnormality will be summarized by treatment group. All post-baseline lab values are being considered. Further details are provided in Section 5.5.3.1 through 5.5.3.4.

- ALT or AST (> 3x ULN and >5xULN)
- TB (> 2x ULN)
- Potential Hy's Law case: (ALT and/or AST > 3xULN with concurrent TB > 2xULN)
- CK (> 5x ULN) and (>10x ULN)
- Fasting Serum Glucose (mg/dL) ( $\leq$ 50, and  $\geq$ 126)
- HbA1C ( $\geq x\%$ ) (the median of HbA1C at baseline)
- Creatinine (change from baseline for >1 mg/dL)
- eGFR (< 15 mL/min/1.73m^2, 15 -< 30 mL/min/1.73m^2)
- Hgb (g/dL) (decrease from baseline for  $\geq 2$  g/dL)
- Hgb (<8 g/dL)

Confidential

Page 24 of 38

Version 1.3, July 23, 2019 Statistical Analysis Plan

• Table 2: Clinical Laboratory Parameters (Safety)

The number and percentage of patients with laboratory abnormalities (i.e., laboratory values outside the stated laboratory normal range) will be summarized at each time point (i.e., including baseline and post-baseline time points) for each laboratory parameter. The determination of laboratory abnormalities will take into account any unscheduled

Confidential

Page 25 of 38

Esperion Therapeutics, Inc.Version 1.3, July 23, 2019Protocol: 1002FDC-058Statistical Analysis Plan

laboratory assessments. Additional lab-related summaries will be provided as follows for hepatic safety, musculoskeletal safety, diabetes and glycemia, and renal safety.

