8. SELECTION AND WITHDRAWAL OF SUBJECTS

8.1. Subject Inclusion Criteria

Subjects must satisfy all the following criteria at Visit S1 (unless otherwise specified) for enrollment in the study:

1. The subject must be willing to provide written informed consent before any study specific procedures are performed;
2. The subject must be aged 18-75 years or be of legal age of majority based on regional law, whichever is older;
3. The subject must have a history of T2D for 6 months or greater; and must be currently taking stable diabetes medication for 3 months or greater with HbA_{1C} between 7% and 10% at Visit S1;
4. The subject must have a fasting calculated LDL-C level >70 mg/dL at Visit S1;
5. The subject must have a fasting calculated LDL-C level between 100 and 220 mg/dL at Visit S3 after washout of all LMT;
6. The subject must clinically stable and suitable to undergo washout of all LDL-C-lowering drugs and nutritional supplements for 17 weeks (with potential for 1-week extension if repeat assessments described in the protocol are required) based on investigator assessment;
7. The subject may be male or female. Women must not be pregnant (or planning to become pregnant within 30 days after the last dose of IMP) or lactating and must be:
 - a. Naturally postmenopausal, defined as ≥ 1 year without menses and either:
 - i. ≥ 55 years old, or
 - ii. < 55 years old with a follicle-stimulating hormone (FSH) level ≥ 40.0 IU/L;
 - b. Surgically sterile by hysterectomy, bilateral oophorectomy, and/or tubal ligation; or
 - c. Willing to use 1 acceptable method of birth control if of childbearing potential unless the subject agrees to follow the definition of true abstinence. The minimal requirement for use of acceptable contraception is from the time the informed consent form (ICF) is signed, during the study period, and for at least 30 days after the last dose of IMP. Acceptable methods of birth control include:
 - i. placement of an intrauterine device (IUD) with or without hormones,
 - ii. established use of oral, implanted, topical, or injectable, or hormonal method of contraception associated with inhibition of ovulation,
 - iii. barrier methods, including condom or occlusive cap with spermicidal foam or spermicidal jelly,
 - iv. vasectomized male partner who is the sole partner for the subject, or

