^b Subject must have a fasting calculated LDL-C level between 100 and 220 mg/dL after 5-week washout of all LDL-C-lowering drugs and nutritional supplements. If TG level is >400 mg/dL, a repeat assessment may be obtained; the repeat assessment will be used to determine study eligibility and screening will be extended by 1 week.

^c Weight will be measured on a calibrated scale in the morning while fasting, in street clothing, and after voiding. BMI will be calculated using height from Visit S1 and measured weight at respective visits.

^d A single 12-lead ECG will be obtained after the subject has rested quietly in the supine position for at least 10 minutes

^e Systolic blood pressure, diastolic blood pressure, and pulse rate will be obtained after the subject has been seated quietly for at least 5 minutes in a chair with the back supported, the feet flat on the ground, and the arms bared and supported at heart level.

- ^f Pregnancy tests will be obtained for women of childbearing potential and for surgically sterile women; FSH level will be obtained for women <55 years old and ≥1 year without menses.
- ^g Basic fasting lipid panel includes calculated TC, calculated LDL-C, HDL-C, calculated non-HDL-C, and TGs.
- ^h Special lipids and other biomarkers include apoB, hs-CRP, glucose, [REDACTED] and HbA_{1c}.
- ⁱ Coagulation panel (see [Table 3](#)) will be performed only at Visit S1/Day -42 unless the subject is receiving an anticoagulant agent in which case the coagulation panel will be repeated at Visit T1/Day 1 and 3 to 7 days after starting the IMP.
- ^j The serology assessment includes HbsAg and HCV-AB.
- ^k Clinical safety laboratories include hematology, clinical chemistry, and urinalysis; the required assays are listed in [Table 3](#).
- ^l Reserve blood sample for potential future exploratory biomarkers will be collected at Visits T1 and T3; separated into K2-edta plasma and serum separator tubes; and processed plasma and serum samples will be stored frozen for potential future analysis.
- ^m Subjects will consume 1 serving of Ensure Original Vanilla® breakfast drink (Abbott Laboratories: 220 calories, 32 g of total carbohydrate) at approximately 9:00 AM and site staff will record the time of the start and completion of the meal. The entire serving should be consumed within 5 minutes.
- ⁿ PPG blood glucose sample will be collected 2 hours ± 5 minutes after the subject begins to consume the Ensure breakfast drink

[figure not shown]

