#### 5.5.3.3 Diabetes and Glycemia

For fasting serum glucose and HbA1C (%), a shift table from baseline with the number and percent of patients will be categorized as below:

Fasting glucose: >=126 mg/dL 100-<126 mg/dL, 50-<100 mg/dL, and <50 mg/dL; HbA1C (%) <8% and >= 8% at baseline, and <7% and >= 7% at post baseline visits. These categories may be adjusted depending on observed data. These tables will be summarized by treatment groups.

Descriptive summary for fasting serum glucose and HbA1C will be provided by treatment group at each scheduled visit.

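### The HbA1c safety flag is set at the baseline median, so it marks about half of subjects with no drug effect, and the HbA1c shift table does not repair it

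*SAP*

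**What the plan says.** SAP 5.5.3 (Laboratory Evaluations) lists laboratory abnormalities to be summarised by treatment group for the AESI evaluation. The HbA1c item is a value at or above x%, where x is "the median of HbA1C at baseline". The fasting glucose item has cuts at or below 50 and at or above 126 mg/dL. The section states that "All post-baseline lab values are being considered". Neither glycaemic item mentions the subject's own baseline. In the same list, the creatinine item and one of the two haemoglobin items are defined by change from baseline.

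The SAP does not say whether the median is pooled or taken per arm, or whether one qualifying value is enough.

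For fasting glucose and HbA1c, SAP 5.5.3.3 (Diabetes and Glycemia) adds that "a shift table from baseline with the number and percent of patients will be categorized as below". The glucose table uses the same categories throughout, including one at 126 mg/dL and above. The HbA1c table splits at 8% at baseline but at 7% post-baseline, and the categories may be adjusted once data are seen.

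Protocol 8.1 requires HbA1c "between 7% and 10% at Visit S1". Protocol Appendix 1 schedules HbA1c and glucose, within the special lipids and other biomarkers panel, at Day 1 (T1), Week 4 (T2) and Week 12 (T3).

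**The concern.** SAP Appendix 2 names the relevant AESI category as onset or worsening of diabetes. Every subject already has type 2 diabetes, so the laboratory flag can only usefully show worsening. A cut at the centre of the sample's own baseline distribution mainly records who entered with a high value. A stable subject at 8.6% is flagged, while a subject who rises from 7.1% to 7.9% is not flagged if the median is 8.0%.

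The shift table is where one would look for the missing baseline information, but its HbA1c cuts differ between the two times. A subject stable at 7.5% and one who rises from 7.1% to 8.9% fall in the same cell: below 8% at baseline, at or above 7% afterwards.

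At stake is the usefulness of the two categorical HbA1c safety displays. Neither separates subjects who worsened from subjects who stayed the same.

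**Working it through.** The documents state no expected flag rate, so there is no planned figure to reproduce.

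**Step 1: one visit, no distributional assumption.** Let m be the median baseline HbA1c. By definition P(baseline ≥ m) ≥ 0.5. If the distribution does not change, P(post-baseline ≥ m) ≥ 0.5 as well. With the SAP's 78 subjects per arm, that is about 78 × 0.5 = 39 flagged per arm at a single visit.

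**Step 2: either visit, and who is flagged.** This needs assumptions, because the documents give only the entry range. Underlying HbA1c is truncated normal on 7–10% (Protocol 8.1), with mean parameter 7.8, 8.0 or 8.5 and SD 0.8 or 1.0. Independent within-subject variation of SD 0.2, 0.3 or 0.5 is added at T1, T2 and T3. Values are rounded to 0.1, the median is pooled, any qualifying value counts, and there is no drug effect or drift. Eighteen scenarios were simulated with 400,000 subjects each. Selected rows, including those that set the ends of the ranges:

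| Mean, SD, within-subject SD | Median | Flagged at Week 12 | Flagged at either visit | Of those flagged at Week 12, already ≥ median at baseline | Of baseline <8%, ≥7% at Week 12 |
|---|---|---|---|---|---|
| 7.8, 0.8, 0.5 | 8.0 | 51.6% | 65.8% | 72.2% | 85.2% |
| 7.8, 1.0, 0.2 | 8.1 | 50.3% | 55.8% | 88.9% | 94.8% |
| 7.8, 1.0, 0.5 | 8.1 | 51.2% | 64.0% | 74.9% | 84.8% |
| 8.0, 0.8, 0.5 | 8.1 | 53.1% | 66.8% | 74.3% | 86.7% |
| 8.5, 0.8, 0.2 | 8.5 | 52.5% | 58.4% | 88.9% | 97.1% |
| 8.5, 1.0, 0.2 | 8.5 | 52.3% | 57.4% | 90.2% | 96.1% |
| All 18 scenarios | 8.0–8.5 | 50–53% | 56–67% | 72–90% | 85–97% |

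Without rounding, the last four ranges become 50%, 55–64%, 72–90% and 83–96%. Per arm of 78, the either-visit rate is 78 × 0.56 = 44 to 78 × 0.67 = 52 subjects.

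**Step 3: response to a true shift.** Adding 0.3 percentage points to every Week 12 value moves the median flag from 50–53% to 64–69%. A within-subject rise of at least 0.5 points, used only as an example, moves from 6–26% to 30–42%. With 78 per arm and z = difference / √[(p₁(1−p₁) + p₂(1−p₂))/78]:

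- Median flag, best case: (0.678 − 0.507)/0.0775 = 2.2. Worst case: (0.643 − 0.521)/0.0786 = 1.6.
- Within-subject rise, in the same two scenarios: (0.299 − 0.057)/0.0581 = 4.2 and (0.416 − 0.261)/0.0748 = 2.1.

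No test of the flag is planned; z only measures how well each definition separates a shifted arm from an unshifted one.

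**Step 4: fasting glucose.** The documents give no distribution. With assumed total SD 35–45 and within-subject SD 15–25 mg/dL, the either-visit rate at or above 126 mg/dL is 41–48% for a mean of 110, 52–60% for 120, and 58–97% for means of 126–170.

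**The case against.** **Other planned outputs use baseline.** This stands. SAP 5.5.3 summarises change and percent change for fasting glucose and HbA1c. SAP 3.3 makes HbA1c change a secondary endpoint, and SAP 5.4 analyses HbA1c and fasting glucose like the primary endpoint, that is, by ANCOVA with baseline as covariate (SAP 5.3.1). Glycaemic adverse events are summarised separately in SAP 5.5.2. A reader might infer that a real glycaemic signal would be swamped. The documents do not support that: a mean worsening would be examined elsewhere, and Step 3 shows that even the median flag responds to one.

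**There is no bias between arms.** This also stands if one pooled cut is used. The flag is shown by randomised treatment group, and its background rate is expected to be the same in each. A per-arm median would give the arms different thresholds, which is one reason to settle the definition.

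**Glucose is already covered.** Largely right. A reader might infer that both glycaemic flags share the fault and that half or more are flagged on each. The glucose shift table uses 126 mg/dL at both times, so new crossings can be read from it. The size of the glucose background rate rests on a distribution that the documents do not give. What remains is only that the AESI count is not split by baseline status.

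**Absolute cuts are normal in this list.** True of the liver, CK, eGFR and one haemoglobin item, but there the entry criteria (Protocol 8.2) keep most subjects off the flagged side: ALT or AST at or above 2 × ULN excluded against a flag above 3 ×, unexplained CK above 3 × ULN excluded against above 5 ×, eGFR below 30 excluded against flags below 30, haemoglobin below 10 g/dL excluded against below 8. For HbA1c the entry range places the cut in the middle of the sample. SAP 5.5.3.1 and 5.5.3.2 also split the liver and CK counts by normal or abnormal baseline.

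**The shift table may be meant to show attainment of less than 7%, and its cuts may be adjusted.** Possibly, but then it describes improvement, and cuts chosen after the data are seen are not prespecified.

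**A 0.5-point rise has no source in the documents.** Agreed; the amount is for the sponsor to set.

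**Conclusion.** The point holds for HbA1c. As a marker of worsening, the median cut is non-specific and relatively insensitive. That at least half are flagged at one visit follows from the definition of a median, provided the HbA1c distribution does not move; a general fall in all arms would lower the rate. The other HbA1c figures in Step 2 depend on the assumed distributions, and the either-visit rate also on reading the SAP as counting any qualifying value. The unequal shift-table cuts leave the same gap, because stable and worsening subjects share a cell.

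This is a weakness in descriptive safety displays. It does not affect the primary analysis or bias the arm comparison, and it does not leave the trial without a baseline-adjusted view of HbA1c. For fasting glucose only a presentational change is warranted. It is worth correcting because the correction is cheap and makes the flag measure what its AESI category is about.

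**What to change.** In SAP 5.5.3, replace the median-based HbA1c item with an increase from the subject's own baseline of a prespecified amount. The sponsor should set the amount; 0.5 percentage points is only an example. State whether one qualifying post-baseline value is enough.

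In SAP 5.5.3.3, use the same HbA1c categories at baseline and post-baseline, and fix them in advance.

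For fasting glucose at or above 126 mg/dL, keep the cut and present the AESI count separately for subjects below 126 and at or above 126 at baseline, following the SAP's approach for ALT, AST, TB and CK.

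The cost is SAP wording and one or two tables, with no new data. The one real decision is the size of the HbA1c rise. It is a judgement and must be fixed before unblinding. A small threshold still picks up ordinary variation: the 0.5-point example flags 6–26% at Week 12 with no effect under the assumptions above.

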#### 5.5.3.1 Hepatic Safety

For liver-associated enzymes and total bilirubin (TB), the number and percent of patients with abnormal values for ALT (>  $3 \times ULN$ , >  $5 \times ULN$ ), AST (>  $3 \times ULN$ , >  $5 \times ULN$ ), and TB (>  $2 \times ULN$ ) will be summarized by overall, normal baseline ALT/AST/TB and abnormal baseline ALT/AST/TB for overall safety analysis set.

Hy's law criteria (>  $3 \times$  upper limit of normal [ULN] for either ALT or AST, with accompanying TB >  $2 \times$  ULN,) will also be applied to the data; any potential Hy's law cases will be listed.

A separate listing for direct TB will be provided for those who have Gilbert's syndrome.

#### 5.5.3.2 Musculoskeletal Safety

CK levels will be summarized by the value and change from baseline in the value, by treatment group and visit as well as baseline eGFR category. In addition, the number and percent of patients with abnormal CK values (>5 x ULN, > 10 x ULN) will be summarized for overall safety analysis set. These summaries of patients with abnormal CK will be performed overall, normal baseline CK, and abnormal baseline CK.

#### 5.5.3.3 Diabetes and Glycemia

For fasting serum glucose and HbA1C (%), a shift table from baseline with the number and percent of patients will be categorized as below:

Fasting glucose: >=126 mg/dL 100-<126 mg/dL, 50-<100 mg/dL, and <50 mg/dL; HbA1C (%) <8% and >= 8% at baseline, and <7% and >= 7% at post baseline visits. These categories may be adjusted depending on observed data. These tables will be summarized by treatment groups.

Descriptive summary for fasting serum glucose and HbA1C will be provided by treatment group at each scheduled visit.

#### 5.5.3.4 Renal Safety

By-visit summary and shift tables of eGFR by baseline category will be provided by treatment group.

In addition, renal function abnormality will be identified as: (1) A creatinine change from baseline of > 1 mg/dL (2) eGFR value <30 mL/min/1.73m^2. A shift table from baseline with the number and percent of patients using the two categories will be presented.

Confidential

Page 26 of 38

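### The SAP's two renal flags are absolute cut-offs that a doubling of creatinine can escape, and the shift table planned on them has almost no baseline variation to shift from

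*SAP*

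**What the plan says.** SAP 5.5.3.4 (Renal Safety) gives two rules: "renal function abnormality will be identified as: (1) A creatinine change from baseline of > 1 mg/dL", and an eGFR below 30 mL/min/1.73 m². It then says: "A shift table from baseline with the number and percent of patients using the two categories will be presented". The laboratory list for adverse events of special interest in SAP 5.5.3 repeats the creatinine cut-off and adds eGFR bands of below 15 and of 15 to below 30. Neither document has a creatinine criterion expressed as a multiple of the subject's own baseline.

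The plan has other renal displays:
- SAP 5.5.3.4 opens with "By-visit summary and shift tables of eGFR by baseline category will be provided by treatment group". SAP 5.2.4 defines the bands: normal 90 or more, mild 60-89, moderate 30-59, severe 15-29.
- SAP 5.5.3 has continuous laboratory parameters "summarized using descriptive statistics for the observed value and the change, percent change from baseline", and SAP 5.1 includes minimum and maximum among the descriptive statistics.
- SAP 5.5.3 counts subjects outside the laboratory normal range at each time point, unscheduled tests included. Creatinine is in the chemistry panel (protocol Table 3).
- The Renal Safety block of SAP 5.5.2 says "Baseline eGFR and values of CK will be summarized by treatment group and by baseline eGFR categories". It has no creatinine summary.

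**The concern.** Renal disorders are a named group of events of special interest (SAP Appendix 2), and the two rules are the SAP's explicit definition of a renal laboratory abnormality. A fixed rise of more than 1 mg/dL is a small relative change for a subject who starts high and a very large one for a subject who starts at 0.6 mg/dL. An eGFR below 30 is a long way from a normal starting value. A subject with good renal function can therefore lose much of it without being counted. The liver and CK flags are tiered multiples of the upper limit of normal and are split by normal or abnormal baseline (SAP 5.5.3.1, 5.5.3.2). Creatinine has one absolute tier.

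The display is a separate problem. A shift table needs a baseline state and a later state, and a rule that is itself a change from baseline has no baseline state. At stake is how far a clean two-rule table can be relied on. Alpha, power and the primary analysis are not affected.

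**Working it through.** The plan gives no figure to reproduce. A doubling of creatinine is my benchmark and appears in neither document.

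**Inputs**
- From the documents: creatinine rise above 1 mg/dL and eGFR below 30 (SAP 5.5.3.4); MDRD as the eGFR formula (protocol 8.2 and 11.6.1); eGFR below 30 excluded at Visit S1 (protocol 8.2); laboratory baseline as the last value before first dose (SAP 5.5.3).
- Assumed: eGFR = 175 × Scr^-1.154 × age^-0.203, × 0.742 for women, race factor 1 in the examples. The documents do not print these coefficients.

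**Rule 1 (needs no outside input).** Doubling from baseline b adds b, so the rule fires only if b > 1.0. Thus 0.6 to 1.2 (+0.6), 0.8 to 1.6 (+0.8) and 1.0 to 2.0 (+1.0, not above 1) all go unflagged.

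**Rule 2.** Doubling multiplies eGFR by 2^-1.154 = 0.449. It takes eGFR below 30 only if baseline is below 30 / 0.449 = 66.8. With exponents from 1.0 to 1.209 this limit runs from 60.0 to 69.4.

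**Both rules, age 60**

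| Subject | Creatinine, mg/dL | eGFR before and after | Rule 1 | Rule 2 |
|---|---|---|---|---|
| Man | 1.0 to 2.0 | 76.2 to 34.3 | no | no |
| Woman | 0.8 to 1.6 | 73.2 to 32.9 | no | no |
| Man | 1.1 to 2.2 | 68.3 to 30.7 | yes | no |
| Woman | 0.9 to 1.8 | 63.9 to 28.7 | no | yes |

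A doubling is missed only when both conditions hold: baseline creatinine 1.0 mg/dL or less, and baseline eGFR about 67 or more. For baseline creatinine of 0.6 to 0.8 mg/dL at ages 50 to 70, a 2.1- to 2.7-fold rise is needed before either rule fires.

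**Shift table, rule 1.** Every subject's change from baseline is zero at baseline, so there is one baseline level by construction.

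**Shift table, rule 2.** Eligibility is judged at S1, but baseline is the last pre-dose value, so a baseline below 30 is possible though rare. With an assumed within-subject creatinine CV of 5 to 8%, a subject at eGFR 31 on S1 has about a 35 to 40% chance of a later baseline below 30; at 40 the chance is 0 to 1%.

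**Category shift table.** A doubling takes any baseline eGFR from 60 up to 60 / 0.449, about 133, below 60. The first man in the table therefore appears as mild to moderate. So does a fall from 61 to 59, which needs a creatinine rise of only (61/59)^(1/1.154) - 1 = 2.9%.

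**The case against.** The strongest reply is that the two flags are an addition to other renal displays. A doubling from eGFR 60 to about 133 shows as a category shift to moderate or worse. It shows as a maximum of at least +100% in the creatinine percent-change statistics. A value of 2.0 mg/dL is counted as out of range under any upper limit below 2.0, although 1.2 mg/dL might not be. The renal preferred terms also include raised creatinine and reduced glomerular filtration rate.

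All of this stands, and it limits the point to the two-rule table and the matching rows of SAP 5.5.3. A reader might infer that the SAP as a whole cannot see renal harm; its other displays contradict that. What those displays lack is a count: the maximum shows one extreme per arm, the out-of-range count ignores the subject's own baseline, and the category shift mixes large and trivial falls.

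Three other stronger readings also lack support:
- That the rules miss doublings in most subjects with normal or mildly reduced function. The documents give no creatinine or eGFR distribution. Simulation over assumed populations (mean eGFR 75-95, SD 15-20, 40-50% women, 10-30% Black, mean age 59, MDRD constant 175 or 186) gave 89-99% missed at eGFR 90 or more but 40-72% in the mild band.
- That both rules have strictly one baseline level. This is true only of the creatinine rule. Its table would still give a usable count under a misleading title.
- That CK in the Renal Safety block is a slip for creatinine. CK by eGFR category appears consistently in protocol 14.8 and SAP 5.5.2 and 5.5.3.2. It is duplication, and the documents do not show it to be an error.

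**Conclusion.** The point holds for the two-rule table. That rule 1 misses any doubling from 1.0 mg/dL or below follows from the SAP text alone. That rule 2 then also misses it at a baseline eGFR of about 67 or more (60 to 69 over the exponents tried) rests on the assumed MDRD coefficients. How many subjects of this trial fall in that region cannot be said from the documents. A zero in this table would not by itself support a conclusion of renal safety, and the shift format should not be used for a change-from-baseline rule. This is a worthwhile correction to a descriptive safety display, limited in reach because other tables carry part of the signal.

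**What to change.** 1. In SAP 5.5.3 and 5.5.3.4, replace the two-rule shift table with counts and percentages by arm of subjects with any post-baseline creatinine at least 1.5 times and at least 2 times their own baseline, and with an eGFR fall of at least 30% from baseline. Keep the two existing cut-offs as further rows.
2. Keep the eGFR category shift table.
3. In the Renal Safety block of SAP 5.5.2, add serum creatinine by baseline eGFR category. CK may stay, although it repeats 5.5.3.2.
4. State how eGFR after S1 is derived from scheduled creatinine, because the schedule of assessments lists the calculation at S1 only.

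The new thresholds are my descriptive choices and change no withdrawal rule. Under the same MDRD exponent a 1.5-fold rise is a 37% eGFR fall (1 - 1.5^-1.154), so the rows overlap and should be read as tiers.

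The cost is SAP wording and one re-programmed table, using safety laboratories already drawn at T1, T2 and T3. The downside is that the flagged counts will look less favourable.
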